11.1.2 Dispensing Visit

- a. Collect/assess all AEs, including serious or significant non-serious AEs
- b. Perform a slit lamp examination (remove the lenses if the subject wore lenses to the visit). Record all slit lamp findings and, at a minimum, sketch the following in the subject's source document:
 - any ungraded finding marked as "PRESENT"
 - any new corneal scars
 - any neovascularization within the central 6 mm of the cornea
 - any corneal staining
 - any corneal infiltrate (record details on the Corneal Infiltrates Evaluation Form [\[Appendix E\]](#))
 - any other graded slit lamp findings Grade 2 or greater
- c. Perform the following assessments without lenses and record in the subject's source document: spherocylindrical refraction, distance BSCVA, and direct ophthalmoscope exam (non-dilated). IOP will be measured using the TonoPen or Goldmann method.
- d. In an effort to ensure the Investigator remains masked, the unmasked designee MUST dispense the lens blister packs. The unmasked designee will dispense 110 lenses per eye to sufficiently maintain a daily disposable modality until the 3-Month Follow-up Visit and record in the Product Accountability Log. A 10 day lens supply per eye can be maintained at the office for each subject's visits should the subject forget to wear their lenses to their follow-up office visits.
- e. Have the subject insert one pair of the study lenses in their eyes. In an effort to ensure the Investigator remains masked, the subject MUST insert the lenses out of the sight of the Investigator.

NOTE: Study lenses should be allowed to equilibrate a minimum of 3 minutes on the eye.

After a minimum of 3 minutes, perform the following assessments and record in the source documentation and applicable eCRF:

- Collect Symptoms/Complaints information using the Symptoms/Complaints Rating Scales in [Appendix A](#)
- distance high contrast lens VA
- over-refraction and distance VA
- lens wettability

- lens centration
- lens movement
- lens rotation
- lens deposits

For each eye, compare the high contrast distance lens VA to the high contrast BSCVA obtained at this visit. If the VA has decreased by 5 letters (0.1 logMAR) or more, explain.

- f. Dispense lens cases. Instruct the subject to place all worn lenses in a lens case (up to 10 pairs of lenses per eye per case) with no solution (dry). The subject will return the lens cases and blister labels to the site at the 1-Week Follow-Up Visit.
- g. Discuss the diary with instructions to complete on a weekly basis. Subjects will be provided with a reminder at every visit to complete the diary to capture wear experience on a weekly basis until they exit the study.
- h. If the subject is discontinued or exited at this visit, complete the Exit Visit eCRF.
- i. Re-emphasize the exclusion criterion stating that if the subject is a female of child bearing potential and is pregnant and or breast feeding, she is ineligible to be a part of the study.

11.1.3 1-Week, 1-Month, and 3-Month Follow-up Visits

- a. If this is an Exit Visit, indicate that on the eCRF and, in addition to completing the appropriate Follow-Up Visit Form, complete the Exit Visit Form. If a subject misses the scheduled follow-up visit and cannot be seen prior to the start of the visit window for the next scheduled follow-up visit, then the visit is considered missed and it should be recorded as a missed visit in the applicable eCRF.
- b. Collect/assess all AEs, including serious or significant non-serious AEs.
- c. If the subject did not wear lenses to the visit, the subject can use a pair from the 10 lenses per eye stored in the office to complete the assessment.
- d. Collect Symptoms/Complaints information using the Symptoms/Complaints Rating Scales in [Appendix A](#) and record them in the source documentation and eCRF.
- e. Evaluate the lenses (while on eye) and record the following assessments in the source documentation and eCRF:
 - distance high contract lens VA
 - over-refraction and distance VA
 - lens wettability
 - lens centration
 - lens movement

- lens rotation
- lens deposits

For each eye, compare the high contrast distance contact lens VA from each respective / current visit (1-Week, 1-Month, 3-Month Follow-up Visits) to the high contrast distance contact lens VA obtained at the Dispensing Visit. If the VA has decreased by 10 letters (0.2 logMAR) or more, record in the subject's source document and explain.

- f. Perform a slit lamp examination (remove the lenses if the subject wore lenses to the visit) and record the following assessments in the source documentation and the eCRF. Record all slit lamp findings and, at a minimum, sketch the following in the subject's source document:
 - any ungraded finding marked as "PRESENT"
 - any new corneal scars
 - any neovascularization within the central 6 mm of the cornea
 - any corneal staining
 - any corneal infiltrate (record details on the Corneal Infiltrates Evaluation Form [\[Appendix E\]](#))
 - any other graded slit lamp findings Grade 2 or greater
- g. Perform the following assessments without lenses and record in the subject's source document: spherocylindrical refraction, distance BSCVA, and direct ophthalmoscope exam (non-dilated). IOP will be measured using the TonoPen or Goldmann method at all visits. Autorefraction will be measured using the standard autorefractor method at the 3-Month Visit only.
- h. The subject will return the worn dry stacked lenses in lens cases and blister foils to the site at each Follow-Up Visit. The unmasked designee will collect the lens cases and put them into the ziploc bag labeled for that visit. The ziploc bag will then be kept in the subject's opaque bag for return to the Sponsor at the end of study. For all visits, except their Exit Visit, dispense lens cases. Instruct the subject to place all worn lenses in a lens case (10 pairs of lenses per eye per case) with no solution (dry) and keep the blister foils to return at their next follow-up visit.
- i. Review diary with instructions to complete on a weekly basis. At the 1-Week visit, provide subject with separate diaries for Month 1, Month 2, and Month 3. Collect the previous month's diary at each follow-up visit.
- j. Re-emphasize the exclusion criterion stating that if the subject is a female of child bearing potential and is pregnant and or breast feeding, she is ineligible to be a part of the study.

If all scheduled visits are performed on time and the subject completes the 3-Month Visit, the Exit Visit will be done at the same time.

11.1.4 Exit Visit

An Exit Visit should be completed for all subjects who complete the study (3-Month Visit) or discontinued the study early (1-Week, 1-Month Visit, or at an Unscheduled Visit).

The Exit Visit will be delayed in the event that there is a complication and the subject needs to be followed up through an Unscheduled Visit.

- a. Indicate status of the subject on the Exit Visit Form. If the status is “Discontinued” or “Non-dispensed,” indicate the PRIMARY exit reason for each eye on the Exit Visit Form.
- b. Collect/assess all AEs, including serious or significant non-serious AEs.
- c. For all dispensed subjects, complete an exit ocular examination without lenses on the eyes. Perform the following assessments: uncorrected distance VA, autorefraction, spherocylindrical refraction, high contrast distance BSCVA, keratometry, dilated fundus exam, and direct ophthalmoscope exam (non-dilated). IOP will be measured using the TonoPen or Goldmann method.
- d. For each eye, compare the Exit Visit high contrast distance BSCVA to the high contrast distance BSCVA obtained at the Screening Visit. If the VA has decreased by 10 letters (0.2 logMAR) or more, record in the subject’s source document and explain.
- e. For each eye, compare the Exit Visit keratometry readings to the Screening Visit keratometry readings. If there is a change of 1.00 D or more, record in the subject’s source document and explain.
- f. The unmasked CRA must collect all worn and unworn lenses, blister foils, and drystacked lens cases from the subject and record and reconcile in the CTM Product Accountability Log. All subject materials will be kept in the subject’s opaque bag to be verified/reconciled by the study monitor before study close out. Once reconciled, the opaque bag can be sealed and returned to Clinical Trial Materials address in Section 10.3.
- g. The Exit Visit eCRF should be completed, in addition to the appropriate Follow-Up Visit Form.

NOTE: All unworn, dispensed, non-dispensed study lenses are to be returned to the Sponsor after the study is complete and the lens reconciliation has been finalized. Worn lenses will be dry stacked in lens cases and returned to Bausch and Lomb. All contact lenses must be accompanied by a CTM Product Accountability Log.

11.1.5 Unscheduled Visits

Additional visits may be scheduled, as necessary, to ensure the safety and well-being of subjects. All additional exams should be fully documented in the source documents and on Unscheduled Visit eCRFs, as appropriate. Visits intended to fulfill scheduled visit requirements that fall outside the designated scheduled visit range, are not Unscheduled Visits. In these cases, the visit data will be collected and transcribed to the appropriate scheduled visit eCRF.

If a subject is seen for multiple visits during a given visit timeframe, the data from the visit that is intended to meet the protocol requirements for the scheduled visit should be captured on the visit eCRF. Where such a determination cannot be made, the first visit within the scheduled visit interval will be used for completion of the protocol required scheduled visit eCRF. Data from any additional visits within a scheduled visit interval will be captured on an Unscheduled Visit eCRF.

Product Dispensing Only (Part of the Unscheduled Visit - used only if lens supply is lost)

If a subject is only seen for an unscheduled lens replacement, a complete exam is not required as long as the subject is not experiencing any problems. In an effort to ensure the Investigator remains masked, an unmasked designee MUST dispense the lens(es) to the subject. Record lenses dispensed in the CTM Product Accountability Log. If study lenses are dispensed, collect the following information in the source document and transcribe to the Product Dispensing Only eCRF Form:

- visit date
- subject ID number
- subject initials
- primary reason for lens replacement
- dispensed lens power

If any assessment is performed, then an Unscheduled Visit Form must be completed instead of a Product Dispensing Only Form.

NOTE: All worn study lenses are to be returned to the Sponsor at the end of the study as directed with the materials provided. Worn lenses will be dry stacked in lens cases and returned to Bausch and Lomb. All contact lenses must be accompanied by a CTM Product Accountability Log.

If a subject is experiencing problems, complete the following:

- a. Indicate the reason for the Unscheduled Visit.
- b. Collect/assess all AEs, including serious or significant non-serious AEs.
- c. Collect Symptoms/Complaints information using the Symptoms/Complaints Rating Scales in [Appendix A](#)

d. Evaluate the lenses (while on eye) and record the following assessments in the source documentation and eCRF:

- distance high contrast lens VA
- over-refraction and distance VA
- lens wettability
- lens centration
- lens movement
- lens rotation
- lens deposits

For each eye, compare the high contrast distance lens VA to the high contrast BSCVA obtained at the Dispensing Visit. If the VA has decreased by 10 letters (0.2 logMAR) or more, record in the subject's source document and explain.

e. Perform the following assessments without lenses and record in the subject's source document: spherocylindrical refraction, distance BSCVA, and direct ophthalmoscope exam (non-dilated). IOP will be measured using the TonoPen or Goldmann method.

f. Perform a slit lamp examination (without lenses). Record all slit lamp findings and, at a minimum, sketch the following in the subject's source document:

- any ungraded finding marked as "PRESENT"
- any new corneal scars
- any neovascularization within the central 6 mm of the cornea
- any corneal staining
- any corneal infiltrate (record details on the Corneal Infiltrates Evaluation Form [\[Appendix E\]](#))
- any other graded slit lamp findings Grade 2 or greater

g. Remind subject to complete the diary on a weekly basis as instructed.

h. Re-emphasize the exclusion criterion stating that if the subject is a female of child bearing potential and is pregnant and or breast feeding, she is ineligible to be a part of the study.

i. The Unscheduled Follow-up Visit eCRF should be completed. If the subject is discontinued or exited at this visit, the Exit Visit Form should also be completed.

11.1.6 Missed Visits

If a subject misses any scheduled follow-up visit and cannot be seen prior to the start of the visit range for the next scheduled follow-up visit, the visit is considered missed.

11.1.7 Study Restrictions

Wearing restrictions are presented in [Appendix B](#).

11.2 Definition of Source Data

All evaluations reported in the eCRF must be supported by appropriately identified source documentation.

11.3 Handling of Subject Withdrawal

No subjects will be replaced on study if a subject withdraws or is removed.

11.4 Evaluation of Effectiveness

11.4.1 Effectiveness Parameters

The primary effectiveness endpoint is the proportion of subjects achieving a contact lens corrected distance logMAR VA of 0.04 or better in both eyes, evaluated at the 1-Week Follow-up Visit.

Other performance criteria for evaluation will be summarized descriptively.

1 Visual acuity

- optimal corrected distance VA measured with the phoropter
- contact lens corrected distance VA

11.5 Evaluation of Safety

11.5.1 Eye Condition

Eye condition criteria include the following, which will be summarized descriptively.

- Slit lamp findings
- Dilated fundus exam findings
- Intraocular pressure

11.5.2 Lens Suitability

- Centration
- Wettability
- Movement

11.5.3 Lens Status

- Deposits

11.5.4 Visual Acuity

- Uncorrected distance VA

11.5.5 Change in Manifest Refraction Between the Screening and Exit Visits

11.5.6 Change in Corneal Curvature Between the Screening and Exit Visits

11.5.7 Adverse Event Definitions

- Adverse Event (AE): any untoward medical occurrence, unintended disease or injury, or untoward clinical signs (including abnormal laboratory findings) in a subject, user or other persons, whether or not related to the investigational medical device. This definition includes events related to the investigational medical device, comparator or the procedures involved. For users or other persons, this definition is restricted to events related to investigational medical devices.
- Adverse Device Effect (ADE): an AE related to the use of an investigational medical device. This definition includes AEs resulting from insufficient or inadequate instructions for use; deployment, implantation, installation, or operation; or any malfunction of the investigational medical device. This definition also includes any event resulting from use error or from intentional misuse of the investigational medical device.
- Serious Adverse Event (SAE) is an AE that:
 - led to death;
 - led to serious deterioration in the health of the subject, that resulted in:
 - a life-threatening illness or injury; or
 - a permanent impairment of a body structure or a body function (eg, blindness); or
 - in-patient or prolonged hospitalization; or
 - medical or surgical intervention to prevent life-threatening illness or injury or permanent impairment to a body structure or a body function;
 - led to fetal distress, fetal death, or a congenital abnormality or birth defect.

NOTE: Planned hospitalization for a pre-existing condition, or a procedure required by the protocol, without serious deterioration in health, is not considered an SAE.

- Unanticipated Adverse Device Effect (UADE): any serious adverse effect on health or safety or any life-threatening problem or death caused by, or associated with a device, if that effect, problem or death was not previously identified in nature, severity or degree of incidence in the investigational plan or application (including a supplementary plan or application), or any other unanticipated serious problem associated with a device that relates to the rights, safety, or welfare of subjects.

11.5.8 Adverse Event

Throughout the course of this study, all efforts will be made to remain alert to possible AEs. The term “AEs” includes both SAEs and Significant Non-Serious Adverse Events. Each are defined below.

If an AE occurs, the first concern will be the safety of the subject and appropriate medical intervention will be made. All AEs (serious AEs and significant non-serious AEs) that occur will be reported in this study.

AEs should be differentiated into device related and non-device related. Any corneal infiltrate, ulcer, neovascularization, etc. shall be presumed to be device related, in the absence of an alternative explanation.

All AEs occurring after signing of informed consent and through the subject’s end of participation in the study must be reported. All AEs must be followed until the event resolves or stabilizes.

All AEs should be photo documented and communicated to the CRO and Sponsor in electronic form.

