11.5.8.2 Significant Non-Serious Adverse Events

Significant Non-Serious Adverse Events should include:

- Peripheral non-progressive non-infectious corneal ulcers;
- All symptomatic corneal infiltrative events;
- All cases of corneal staining greater than or equal to Grade 3;
- A temporary loss of 2 or more lines of BSCVA (for greater than or equal to 2 weeks);
- Neovascularization cases equal to Grade 2 or greater;
- Any ocular event that necessitates temporary lens discontinuation of greater than or equal to 2 weeks.

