12.3.3.2 Treatment-emergent or Post-treatment Adverse Events

An in-text table of overview of treatment-emergent or post-treatment adverse events subjects with any treatment-emergent or post-treatment AE, subjects with any severe treatment-emergent or post-treatment AE, subjects with any treatment-emergent or post-treatment serious AE, subjects with any treatment-emergent or post-treatment AE leading to permanent treatment discontinuation, or any treatment-emergent or post-treatment AE leading to death (only if death occurred), will be produced by treatment group.

Subjects presenting with treatment-emergent or post-treatment AEs will be listed sorted by treatment group, primary system organ class (SOC), and preferred term (PT).

Treatment-emergent or post-treatment AEs will be summarized by treatment group, tabulating:

- The number and percent of subjects with at least 1 treatment-emergent or post-treatment AE within each and over all SOC(es);
- The number and percent of subjects experiencing each PT in each SOC;
- The number of occurrences of all PT(s) within each and over all SOC(es);
- The number of occurrences of each PT in each SOC.

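### The protocol uses two AE scopes (broad in Section 11.5.7 and the visit procedures, narrow in Sections 11.5.8 and 11.5.8.6), and Section 12.3.3 does not say which one feeds the AE tables

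*Combined protocol and SAP*

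**What the plan says.** **Broad scope.** Section 11.5.7 defines an AE as "any untoward medical occurrence, unintended disease or injury, or untoward clinical signs (including abnormal laboratory findings) in a subject, user or other persons", related to the device or not. Sections 11.1.2, 11.1.3, 11.1.4 and 11.1.5 tell sites to collect all AEs and name the serious and significant non-serious ones as included. Table 1 schedules AEs at every visit.

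**Narrow scope.** Section 11.5.8 says that the term "includes both SAEs and Significant Non-Serious Adverse Events. Each are defined below", and then gives the reporting rule: "All AEs (serious AEs and significant non-serious AEs) that occur will be reported in this study". Section 11.5.8.6 opens its reporting procedure with the same parenthesis and sets beside it a Medical Treatment (non-AE) class. Section 11.5.8.4, whose heading also refers to non-adverse events, covers prescription treatment of an ocular condition.

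**The significant non-serious class.** Section 11.5.8.2 is a list of six ocular items. Examples are "All symptomatic corneal infiltrative events" and "All cases of corneal staining greater than or equal to Grade 3". The others are peripheral non-infectious ulcers, neovascularization of Grade 2 or more, a BSCVA loss of 2 or more lines lasting at least 2 weeks, and ocular events that keep the subject out of lenses for at least 2 weeks.

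**The analysis.** Section 12.3.3.1 lists the AEs reported in the study. Section 12.3.3.2 tabulates treatment-emergent and post-treatment AEs by treatment group, system organ class and preferred term. Neither says whether the input is every event under Section 11.5.7 or only the two classes in Section 11.5.8.

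**The concern.** Safety is part of the stated objective (Section 6.1), and the AE tables are a main place where a reader will look for it. If a site follows the reporting rule as written, an event can meet the protocol's AE definition and still not be reported as an AE. If another site follows the visit procedures, the same event is recorded. The tabulated incidence then mixes true frequency with the site's reading of the text, and a low count could mean either few events or a narrow filter. Events that were never recorded cannot be reliably recovered at the analysis stage.

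**Working it through.** No figure in the plan bears on this point, so the check is a comparison of text.

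**Step 1. Is the narrow wording an isolated slip?** No. The parenthesis that equates AEs with the two classes stands in Section 11.5.8 and again in Section 11.5.8.6, which is the operative reporting procedure. The Medical Treatment (non-AE) class makes sense only if some ocular conditions that need prescription treatment are not AEs. Under Section 11.5.7 such a condition is an AE.

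**Step 2. Which events fall between the two scopes?** Take four events and assume that none has a feature on the serious list in Section 11.5.8.1.

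| Event | AE under 11.5.7? | On the 11.5.8.2 list? | Recorded elsewhere? |
|---|---|---|---|
| Asymptomatic corneal infiltrate | Yes, as an untoward sign | No, only symptomatic ones are | Yes: slit lamp record and the infiltrate form |
| Corneal staining, Grade 2 | Yes, if judged untoward | No, the list starts at Grade 3 | Yes: slit lamp record |
| Conjunctivitis, less than 2 weeks out of lenses | Yes | No | As Medical Treatment (non-AE) if a prescription is needed; signs at slit lamp if seen at a visit |
| Non-serious systemic illness | Yes | No, the list is ocular only | Not as an event; any medicine taken is collected under Section 9.2 |

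All four can meet the definition, and all four fall outside the narrow reporting rule.

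**Step 3. Does the analysis section settle the scope?** No. Section 12.3.3.1 works from what was reported, so the tables take on whichever scope each site used. A layout by system organ class suits full capture but does not require it.

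**Step 4. What do the other safety summaries recover?** The visit procedures call for recording corneal staining, infiltrates and other slit lamp findings of Grade 2 or more. Section 11.5.1 summarizes slit lamp findings descriptively, and Section 12.3.1.1 does this in general by treatment group and visit. The first two rows of the table would therefore still be seen by arm, though not as coded AEs. Systemic events would not be.

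**Step 5. Can the omission be sized?** No. The documents give no AE rates. Multiplying an assumed share of affected subjects by the 244 planned only restates the assumption: 2% gives 244 × 0.02 = 4.9 subjects and 20% gives 244 × 0.20 = 48.8. Neither share has support in the documents.

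**The case against.** The strongest reply is that the protocol as a whole points to the broad scope. The visit procedures are the instructions that sites follow day to day, and they treat the two classes as subsets. In Section 11.5.8 the word used is one of inclusion, which need not exclude anything else, and the sentence that begins "All AEs occurring after signing of informed consent and through" the end of participation carries no parenthesis. The same section presumes any corneal infiltrate to be device related, with no requirement of symptoms. Section 11.5.8.2 says what the class should include, which need not be exhaustive. Section 11.5.8.5 has a Mild grade for events that need no treatment, and the pregnancy guidance in Section 11.5.8.6 expects some non-ocular events to be recorded as AEs. This stands to the extent that the scope is ambiguous and not settled as narrow. It does not remove the two parentheses or the non-AE treatment class.

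Three stronger readings are tempting, and the documents do not support them:

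- A reader might infer that the AE tables would omit most of the milder ocular events. No rate in the documents supports *most*, and the broad passages mean that some or all sites may capture everything. *Could omit* is as far as the text goes.
- A reader might infer from the severity scale that Section 12.3.3 tabulates AEs by mild, moderate and severe. It does not. The overview in Section 12.3.3.2 names any AE and any severe AE; the three-grade scale is an investigator rating in Section 11.5.8.5.
- A reader might infer that the comparison between arms is biased. Randomization is stratified by site (Section 9.1), so differences between sites in how the text is read should not by themselves favor one arm.

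It is also fair to say that broadening the scope has a cost beyond data entry. Section 11.5.8 asks for photographs and follow-up to resolution or stabilization for all AEs, and these duties would extend to every minor or systemic event unless that text is revised too.

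**Conclusion.** The contradiction is real and sits in operative text. Sections 11.5.8 and 11.5.8.6 cannot be followed literally together with Section 11.5.7 and the visit procedures. Under the narrow reading, the AE tables could leave out sub-threshold ocular events and non-serious systemic events that the protocol itself defines as AEs, and the incidence in both arms could be understated and hard to interpret. The conclusion rests on one assumption: that at least some sites follow the reporting rule as written. The size is unknown. The loss is limited for corneal signs, which appear in the slit lamp summaries, and is greatest for non-serious systemic events, which have no such second summary. The primary effectiveness analysis is not affected.

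**What to change.** 1. Reconcile Sections 11.5.7, 11.5.8, 11.5.8.4, 11.5.8.6 and the visit procedures in Sections 11.1.2 to 11.1.5 to one AE scope.
2. State that every event meeting the Section 11.5.7 definition is recorded on the eCRF and included in the Section 12.3.3 listings and tables, with serious and significant non-serious events as flagged subsets.
3. Reconcile the Medical Treatment (non-AE) class with that definition, so that an ocular condition under treatment is not both an AE and a non-AE.
4. State which events the 24-hour report to the Medical Monitor (Section 11.5.8.6) and the photograph and follow-up sentences (Section 11.5.8) apply to.
5. If the sponsor intends the narrow scope, change the definition in Section 11.5.7 and the visit procedures to match, and label the AE tables as covering only those two classes.

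The cost is protocol wording and somewhat more AE data entry at sites. Item 4 lets the sponsor say whether the heavier reporting duties should reach minor events.
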